Note: The start of each cycle may occur ± 3 days of the scheduled day in order to accommodate the schedule of the site or subject. For Cycles 1-6, there may be ± 1 day window for the scheduled infusion within the cycle. The EoT visit may occur $+7$ days of scheduled day. After PD is documented, subjects will continue to be followed for survival, second primary malignancies, and subsequent anticancer therapy.

TIME AND EVENTS SCHEDULE: PK AND IMMUNOGENICITY (ALL SAMPLES SHOULD BE SENT TO THE CENTRAL LABORATORY)

	Treatment Phase																	EoT ^d	Follow-up Phase	
	Weekly for 8 infusions				Biweekly for 8 infusions				Once every 4 weeks											
Cycle	Cycle 1				Cycle 2				Cycle 3	Cycle 4	Cycle 5	Cycle 6	Cycle 7	Cycle 9	Cycle 11	Cycle 12	Cycles 13, 15, 17+			
Study Day (Day)	1	8	15	22	1	8	15	22	1	1	1	1	1	1	1	1	1		FU-Wk4 ^d	FU-Wk8 ^d
Visit Window (day)	0	±1	±1	±1	±3	±1	±1	±1	±3	±3	±3	±3	±3	±3	±3	±3	±3	+7	±7	±14
Study Drug Administration ^a	X	X	X	X	X	X	X	X	X	X	X	X	X	X	X	X	X			
Pharmacokinetic Samples																				
Before Infusion (within 2 hours before the start of infusion)	X	X		X	X			X	X	X	X	X	X	X	X	X	X ^b	X	X ^c	X
End of infusion (within 2 hours after end of infusion)	X							X	X											
Immunogenicity Samples (NO additional immunogenicity samples needed and will be taken from PK samples for the planned time points.)																				
Before Infusion (within 2 hours before the start of infusion)	X												X			X		X	X ^c	X

Footnote:

- For complete study drug administration schedule beyond Cycle 3, refer to the main Time and Events Schedule.
- Samples will be collected at every other dose from Cycle 13+, ie, at Cycle 13, 15, 17, etc.
- If EoT sample is collected within 3-5 weeks after the last dose, ie, the window of FU-Wk4 visit, then FU-Wk4 sample does not need to be collected.
- The EoT is within 30 days (+7) of the last dose. FU-Wk4 and FU-Wk8 is 4 weeks (±7 days) and 8 weeks (±14 days) from the last dose, respectively.

ABBREVIATIONS

ADCC	antibody-dependent cell-mediated cytotoxicity
ADCP	antibody dependent cellular phagocytosis
AE	adverse event(s)
ANC	absolute neutrophil count
Anti-HBc	antibodies to hepatitis B core antigen
Anti-HBs	antibodies to hepatitis B surface antigen
BICR	blinded independent central review
CDC	complement dependent cytotoxicity
CI	confidence interval
CIP	Complement Inhibitory Protein
CNS	central nervous system
COPD	chronic obstructive pulmonary disease
CR	complete remission
CT	computed tomography

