7.3. Prohibited Therapies

Use of the treatments listed below is prohibited during the study:

- Prophylactic use of hematopoietic growth factors during Cycle 1
- Other agents that target CD38
- Concurrent radiation therapy is prohibited while on study.
- Administration of commercially available agents with activity against or under investigation for NKTCL, including systemic corticosteroids (≥ 20 mg/day of prednisone or its equivalent per day for more than 7 days during study, unless reviewed/approved by the study responsible physician) (other than those given for IRRs as described in Section 5.3.2) is prohibited.

The sponsor must be notified in advance (or as soon as possible thereafter) of any instances in which prohibited therapies are administered.

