8.1.4. Posttreatment Phase (Follow-Up)

The Follow-up Phase will begin once a subject discontinues study treatment, the date of discontinuation of study treatment is based on the study physician's written confirmation date in the PD form. Subjects who discontinue before PD (for other reasons such as an AE) must continue to have their regularly scheduled scans according to the [T&E Schedule](#) until centrally confirmed PD, death, the start of a new anticancer therapy, withdrawal of consent, lost to follow-up, or the end of the study. After PD is centrally evidenced with study physician's confirmation of PD form, follow-up will occur at least every 8 weeks (± 2 weeks). Subsequent anticancer therapy, second primary malignancies, and survival status will be recorded.

If the follow-up information is obtained via telephone contact, written documentation of the communication must be available for review in the source documents. If the subject has died, the date and cause of death will be collected and documented in the eCRF.

Investigators may recontact the subject to obtain long-term follow-up information regarding the subject's safety or survival status as noted in the informed consent form (refer to Section [15.2.3](#), Informed Consent).

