9.2. Discontinuation of Study Treatment/Withdrawal From the Study

Discontinuation of Study Treatment

If a subject's study treatment must be discontinued, it will not result in automatic withdrawal of the subject from the study. The EoT Visits and Follow-up visit assessments should continue as specified in the [T&E Schedule](#).

A subject's study treatment (daratumumab) should be discontinued if:

- The investigator believes that for safety reasons or tolerability reasons (eg, AE) it is in the best interest of the subject to discontinue study treatment
- The subject becomes pregnant
- The subject withdraws consent for administration of study drug
- The subject initiates treatment with a prohibited medication
- The subject received concurrent (non-protocol) treatment for NKTCL
- The subject experiences unacceptable toxicity, including IRRs described in [Section 5.3](#)

- The subject's dose of daratumumab is held for more than 4 weeks in Cycles 1-6 or for more than 6 weeks in Cycle 7 and beyond (unless sponsor approves continuation)
- The subject experiences PD (see below and [Attachment 6](#)). Relapse from CR is not considered as disease progression.
- Daratumumab becomes commercially available (or when daratumumab can be accessed from another source) for this disease. At this time, the subject will be transitioned from study drug to commercial product and will be withdrawn from the study. In these circumstances, the sponsor and investigator will support transition of the subject to ensure that treatment continues and remains uninterrupted.
- A subject who experiences a second primary malignancy that cannot be treated by surgery or radiotherapy alone must be withdrawn from the study. However, a subject who develops a malignancy that can be cured surgically or with definitive radiotherapy may continue to receive the assigned study treatment and should continue to be followed for subsequent progression of NKTCL.

Subjects should be discontinued from study treatment if they have objective radiological PD based on real time BICR according to LUGANO Classification. Following centrally confirmed radiological PD subjects will be discontinued from study treatment and enter the Follow-up phase.

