For subjects who have PD as evidenced by unambiguous clinical information (eg. pathologically demonstrated as PD), before such subjects discontinue study treatment due to PD, sites will document PD by completing and faxing a PD form to the sponsor as soon as possible and within 48 hours of PD assessment; EoT steps will be performed. The study responsible physician will confirm that treatment should be discontinued. After confirmation from the sponsor, study treatment may be discontinued and the subject can enter into Follow-up phase. If a subject discontinues study treatment for any reason other than PD, then disease assessments should be obtained as specified in the [T&E Schedule](#).

Withdrawal From the Study

A subject will be withdrawn from the study for any of the following reasons:

- Lost to follow-up
- Withdrawal of consent
- Death
- Sponsor terminates the study.

If a subject is considered lost to follow-up, every reasonable effort must be made by the study-site personnel to contact the subject and determine the reason for discontinuation/withdrawal. The measures taken to follow up must be documented.

When a subject withdraws before completing the study, the reason for withdrawal is to be documented in the eCRF and in the source document (refer Section [8.1.4](#) and Section [15.2.3](#) for details on collection of long-term survival status). Study drug assigned to the withdrawn subject

may not be assigned to another subject. Subjects who withdraw will not be replaced. If a subject withdraws from the study before the EoT, assessments should be obtained.

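### Protocol 9.2 takes subjects with certain second primary malignancies out of the study, against its own withdrawal list and follow-up plan; its radiotherapy sentence and the 7.3 radiation ban also need reconciling

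*Protocol*

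**What the plan says.** Protocol 9.2 has two parts. The first, on discontinuing study treatment, opens with the general rule: "If a subject's study treatment must be discontinued, it will not result in automatic withdrawal of the subject from the study". It adds that end-of-treatment and follow-up assessments go on as scheduled. A list of reasons for stopping daratumumab follows, and one bullet reads: "A subject who experiences a second primary malignancy that cannot be treated by surgery or radiotherapy alone must be withdrawn from the study". The bullet's next sentence says that "a subject who develops a malignancy that can be cured surgically or with definitive radiotherapy may continue to receive the assigned study treatment" and should still be followed for progression of the lymphoma.

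The second part is the dedicated withdrawal list, introduced by "A subject will be withdrawn from the study for any of the following reasons". It has four entries: loss to follow-up, withdrawn consent, death, and termination by the sponsor.

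On follow-up, Protocol 3.1 ends the Follow-up Phase at death, loss to follow-up, withdrawn consent or end of study. The Time and Events Schedule has follow-up rows for new malignancy and for survival, and its closing note says that after progression "subjects will continue to be followed for survival, second primary malignancies, and subsequent anticancer therapy". Section 8.1.4 states: "Subsequent anticancer therapy, second primary malignancies, and survival status will be recorded".

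On radiotherapy, Protocol 7.3 states: "Concurrent radiation therapy is prohibited while on study". No exception is given.

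**The concern.** The bullet stands in a list about stopping a drug, but it prescribes leaving the study. A site that follows it to the letter closes the subject's participation at the point where the plan elsewhere wants a new malignancy and its outcome recorded. The subjects affected are those whose second cancer cannot be managed with surgery or radiotherapy alone, which are likely to be the more serious cases. Overall survival is a secondary endpoint. Incomplete survival data in subjects selected by a prognostic event are less benign than the same amount missing at random.

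The companion sentence raises a separate question. A subject whose second malignancy is to be cured with radiotherapy may stay on study treatment under 9.2, but 7.3 prohibits concurrent radiation. A site cannot tell from the text whether continuing is permitted or is a deviation.

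**Working it through.** This is a question of consistency, so the check is mainly a comparison of passages.

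**Does a second malignancy end study participation?**

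| Place | Answer |
|---|---|
| 9.2, bullet in the treatment-stopping list | Yes, if not treatable by surgery or radiotherapy alone |
| 9.2, opening rule | Stopping treatment does not by itself do so; follow-up continues |
| 9.2, withdrawal list (four reasons) | Not listed |
| 3.1, events ending the Follow-up Phase | Not listed |
| 8.1.4, events ending scans for subjects who stop before progression | Not listed by name |
| Time and Events Schedule, follow-up rows and closing note | New malignancy and survival are to be collected |

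One sentence points one way and the other places point the other way.

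**What stops if the bullet is followed literally?** The scheduled contact at least every 8 weeks (schedule footnote k; 8.1.4) stops. Three provisions remain:

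- 9.2 asks for assessments if a subject withdraws before the end-of-treatment visit.
- 9.2 points to 8.1.4 and 15.2.3 for long-term survival status. Section 8.1.4 permits the investigator to recontact the subject but does not require it.
- The consent described in 15.2.3 covers obtaining survival status.

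Survival collection therefore moves from scheduled to discretionary.

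**Which endpoints are exposed?**

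- Response rate: not exposed. SAP 2.8.1 uses all treated subjects, so a withdrawn subject stays in the denominator.
- Overall survival: exposed to incomplete follow-up. SAP 5.3.1 censors at withdrawal for withdrawn consent or loss to follow-up, and otherwise at the last date known alive for subjects alive at analysis. Withdrawal required by the protocol is not named.
- Progression-free survival: partly exposed. Under 8.1.4 scans end at a new anticancer therapy, and SAP 5.3.1 censors before it. If treatment of the second cancer counts as such, imaging would stop anyway; the documents do not say.
- Second-malignancy outcome: exposed directly.

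**How many subjects?** The documents give no incidence, so *q* is an assumption. Expected number = *n* × *q*; chance of at least one = 1 − (1 − *q*)^*n*. Sample sizes are *n* = 32 (Protocol 10.2) and about 32 + 35 = 67 with the expansion.

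| Assumed *q* | Expected, n = 32 | At least one | Expected, n = 67 | At least one |
|---|---|---|---|---|
| 1% | 0.3 | 28% | 0.7 | 49% |
| 2% | 0.6 | 48% | 1.3 | 74% |
| 5% | 1.6 | 81% | 3.4 | 97% |

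If *q* is the rate of any second malignancy, these are upper figures, because only some would trigger the bullet. Per subject the share is 1/32 = 3.1% or 1/67 = 1.5%; two subjects of 32 are 2/32 = 6.3%.

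**Radiotherapy.** Section 9.2 allows study treatment to continue where definitive radiotherapy can cure the second malignancy. Section 7.3 bans concurrent radiation for the time on study. Neither mentions the other.

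**The case against.** The strongest reply is that this is loose drafting whose intent can be recovered. The bullet sits under a heading about stopping daratumumab, its companion sentence concerns study treatment, and the surrounding text keeps subjects in follow-up. That may well be the intent, but the bullet's wording is mandatory and a site would be right to obey it. One could also say that the opening rule excludes only automatic withdrawal, so the bullet is a deliberate exception. If so, the withdrawal list and the Follow-up Phase end points should carry the exception, and they do not.

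A reader might infer that these subjects' outcome and survival are lost, with no end-of-treatment assessment and no date of death. The documents do not support that: 9.2 asks for assessments at early withdrawal and points to survival collection, 8.1.4 permits recontact, and the consent covers survival status.

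A reader might also infer that deaths are under-counted because these subjects are censored at withdrawal. The SAP does not say so. Its censoring at withdrawal is tied to withdrawn consent or loss to follow-up, and SAP 6.2.1 summarises all deaths in the treated population, so a later death that becomes known could still count. What remains is that learning of it is no longer scheduled.

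On radiotherapy, the ban covers concurrent radiation. The protocol provides for dose holds, and 9.2 does not say that daratumumab is given during radiotherapy, so the two can be read together. That makes the point an ambiguity rather than a flat contradiction. The absence of any exception or cross-reference still leaves sites to guess.

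Finally, the numbers are small. Protocol 4.2 excludes active malignancy in the previous 2 years with stated exceptions, the study ends about 9 months after the last subject's first dose, and the survival analyses are descriptive. This stands, and it limits the size of the point.

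**Conclusion.** The inconsistency is real. The second-malignancy bullet in 9.2 conflicts with the section's opening rule, its withdrawal list, the Follow-up Phase end points in 3.1, and the planned recording of second malignancies and survival. Taken literally, it replaces scheduled follow-up with optional recontact for the subjects concerned, which puts overall survival and second-malignancy outcome data at risk.

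The effect is probably small: 0 to 2 subjects, each 3.1% of 32 or 1.5% of about 67. That count is a judgement, because the documents give no rate; at an assumed 5% for any second malignancy, the upper figure with the expansion is 3.4. The response rate and its decision rule do not change. The point is worth making because the correction is nearly free and concerns events that follow-up was set up to capture.

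The radiotherapy passages in 9.2 and 7.3 are ambiguous when read together and need reconciling. No view is taken on which governs.

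**What to change.** Reword the 9.2 bullet so that it does not end study follow-up. The subject should stay in the Follow-up Phase for malignancy outcome and survival, in line with 3.1, 8.1.4 and the withdrawal list in 9.2. Whether and when study treatment stops should remain as the sponsor intends. With that wording, SAP 5.3.1 needs no new overall-survival censoring category, since these subjects would fall under the existing rules.

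Separately, the sponsor should reconcile the radiotherapy sentence in 9.2 with the prohibition in 7.3 and cross-refer the two sections.

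The cost is one bullet and one cross-reference. Follow-up would use the 8-weekly contact already scheduled, so the downside is a few more contacts for few if any subjects.

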9.3. Withdrawal From the Use of Samples in Future Research

The subject may withdraw consent for use of samples for research (refer to Section 15.2.5, Long-Term Retention of Samples for Additional Future Research). In such a case, samples will be destroyed after they are no longer needed for the clinical study. Details of the sample retention for research are presented in the main ICF.

10. STATISTICAL METHODS

Statistical analysis will be done by the sponsor or under the authority of the sponsor. A general description of the statistical methods to be used to analyze the efficacy and safety data is outlined below. Specific details will be provided in the Statistical Analysis Plan.

10.1. Subject Information

The primary analysis population is the safety population, which will include all treated subjects. The pharmacokinetic analyses will be performed on the pharmacokinetic evaluable population. Continuous variables will be summarized using descriptive statistics such as mean, SD, and range. Categorical variables will be summarized using frequency tables. For time-to-event variables, the Kaplan-Meier method will be used for descriptive summaries.

10.2. Sample Size Determination

The study is designed to evaluate the effect of daratumumab on ORR utilizing Simon's 2-stage design. The null hypothesis is that ORR is at most 15%, and the alternative hypothesis is that ORR is at least 30%. With a 1-sided α of 10%, and a power of 78%, a total of 32 subjects are to be enrolled into the study. The stage 1 analysis is to be performed when approximately 15 subjects are enrolled in the study and have sufficient data for response evaluation. The futility criterion of ORR is defined as when at most 1 out of 15 subjects have achieved CR/PR after stage 1 according to Simon's 2-stage design. Future enrollment into stage 2 may be terminated if it is determined during the first stage that the treatment group is considered as ineffective or not well-tolerated. If study proceeds to second stage with a total of 32 subjects with 2 stages combined, the null hypothesis is to be rejected if 8 or more responses are observed.

To achieve 1-sided α of 2.5% and a power of 80%, additional patients (ie, approximately 35 patients) may be enrolled in an expansion phase to confirm the clinical response rate of daratumumab if supported by emerging data.

10.3. Efficacy Analyses

10.3.1. Primary Efficacy Endpoint

Objective response rate (ORR) is defined as the proportion of subjects who achieve CR or PR per Revised Criteria for Response Assessment of Hodgkin and non-Hodgkin lymphoma: LUGANO classification¹² based on BICR. An estimate of the primary efficacy endpoint ORR

will be presented along with a 2-sided 95% exact CI. The number and percentage of subjects falling into each response category will be descriptively tabulated.

10.3.2. Secondary Efficacy Endpoint

Complete response (CR) rate is defined as the proportion of subjects who achieve CR based on BICR and will be analyzed similarly as the primary efficacy endpoint.

Progression-free survival (PFS) is defined as the duration from the date of the first daratumumab dose to the date of progression/relapse based on BICR or death, whichever comes first. For those subjects who are still alive without progression/relapse, PFS will be censored at the last adequate tumor assessment.

Duration of response (DoR) will be duration from the date of the initial documentation of a response to the date of first documented evidence of PD based on BICR (PD; or relapse for subjects who experience CR) or death. For those subjects who are still without progression/relapse, DoR will be censored at the last adequate tumor assessment.

Time to response is defined as the duration from the date of the first dose of daratumumab to the earliest date that a response (CR/PR based on BICR) is first documented. For nonresponders, it will be censored at the date of PD/relapse or the date of the last adequate disease assessment, whichever comes first.

Overall survival (OS) is defined as the duration from the date of the first daratumumab dose to the date of death. For those subjects who are still alive without progression/relapse, OS will be censored at the last date known to be alive.

For time to event endpoints (eg, PFS, OS, time to response, DoR), Kaplan-Meier estimates will be presented. Median along with corresponding 95% CIs will be obtained from the Kaplan-Meier estimates. Analysis for time to response and DoR will be for responders only.

10.4. Pharmacokinetic Analyses

Pharmacokinetic (PK): PK analyses will be performed on the PK-evaluable population, defined as subjects who have received at least 1 dose of daratumumab and at least 1 postinfusion sample.

All serum concentrations below the lowest quantifiable concentration in a sample or missing data will be labeled as such in the concentration database. Concentrations below the lowest quantifiable concentration in a sample will be treated as zero in the summary statistics. All subjects and samples excluded from the analysis will be clearly documented in the clinical study report.

Descriptive statistics will be used to summarize daratumumab serum concentrations at each sampling time point and PK parameters of daratumumab (C_{max} , t_{max} , AUC) following the 1st infusion. Mean serum daratumumab concentration time profiles will be plotted after the first dose of study drug, and composite serum concentration time profiles may also be plotted.

If sufficient data are available, then population pharmacokinetic analysis of serum concentration time data of daratumumab may be performed using nonlinear mixed-effects modeling and may include data from other studies. If the population pharmacokinetic analysis is conducted, then details will be given in a population pharmacokinetic analysis plan and the results of the analysis will be presented in a separate report.

The relationship between derived PK parameters and covariates, such as actual dose, body weight, and selected laboratory parameters, may be evaluated graphically. Further exploratory analyses of PK data may be performed and reported separately.

10.5. Immunogenicity Analyses

The incidence of antibodies to daratumumab (immunogenicity) will be summarized for all subjects who receive a dose of daratumumab and have appropriate samples for detection of antibodies to daratumumab. A listing of subjects whose sample(s) are positive will also be presented. Daratumumab concentrations will be summarized at all immunogenicity time points. The maximum titers of antibodies to daratumumab will be summarized for subjects who are positive for antibodies to daratumumab.

The impact of antibodies to daratumumab on drug exposure and efficacy/safety will be analyzed if there are positive samples.

